As indicated, in addition to the study monitor, the Brain Stimulation Service Director, [name], will review each research chart for completeness and accuracy. He will provide independent confirmation that inclusion and exclusion criteria have been met for each patient enrolled and that there is compliance with all other aspects of the investigational plan and the investigator agreement. Similarly, [name] at the GRU will also review each research chart for completeness and accuracy. He will provide independent confirmation that inclusion and exclusion criteria have been met for each patient enrolled and that there is compliance with all other aspects of the investigational plan and the investigator agreement.

V. Manufacturing Information (PROVIDED BY THE MANUFACTURER)

In the FDA review of the original Spectrum 5000Q FEAST Device IDE application (6/8/05) a number of deficiencies were listed. Several of these related to the modified Spectrum units to be used in the study. These deficiencies are again addressed specifically in Sections V.C, V.D, and V.E.

Because of our preliminary work in humans, we have changed the specifications for the FEAST units from the original application. The modifications to the standard Spectrum for the FEAST IDE will include the following:

- Change voltage limits from 10-400 Volts

This change was approved and included in the ongoing IDE. As noted above, since increasing the voltage cutoff to 400 V there have been no untoward events, including no skin burns.

The 0.3 ms pulse width has been available as part of the standard marketed units since July, 2003 and thus does not constitute a modification or change for the FEAST units. See notes in Section V.C.

Reliability and validity of the manufacturing of these devices is ensured by testing each unit to validate the output of the device. The verification that the Current, Duration, Pulse Width and Frequency are within the acceptable ranges are all tested, recorded and validated in the Manual Test for each device.

Methods of manufacturing are determined by UL, cUL, TUV, ISO 9001 and FDA approvals and are identical to current methods used to manufacture, process, package, store, and install the Spectrum devices.

Facilities and Controls are determined by the UL, cUL, TUV, ISO 9001 and FDA approvals of the device and facility and are identical to current facilities and controls to manufacture, process, package, store and install the Spectrum devices.

RERERENCE APPROPRIATE SECTIONS AND APPENDICES FOR FURTHER DISCUSSION OF THE FOLLOWING DESIGN AND MANUFACTURING REQUIREMENTS:

Design/engineering drawing of device—Reference Appendix A.1 Block Diagram

Rationale for device design—MECTA has been asked to design a modification to the existing approved Spectrum 5000Q for a research study of FEAST.

Device and Performance specifications—The Spectrum hardware specifications are identical with the exception of the rectifier on the stimulus output and a small change to allow delivery currents down to 100mA. See Section V.D for new verification and validation data. Reference Appendix A.2 and Hardware Modification Section (Section V.B).

Description of Materials- Reference Hardware Modification Section (diodes and electrodes) (Sections V.B and V.E)

Description of Function- Reference Appendix A.2 Block Diagram

Validation Testing for Subsystems and Main System- Reference Appendix A.3 and Section V.D.

Manual Test – which verifies and validates all of the settings.

A. Software Modification

The devices used for the FEAST research are modified versions of MECTA's standard Spectrum 5000 Q product. The Spectrum unit itself has been modified to allow delivery of a unidirectional pulse train (all pulses have current flow in the same direction) and to change the lowest delivery current from 500 mA down to 100 mA. The details of the hardware modifications are covered in a separate document. This document describes the software changes to the Spectrum 5000 Q units.

The software changes provide control and support for the following:

1. Enabling or disabling the hardware unidirectional feature (addition of a menu option), and
2. Extending the lower end of the delivery current range from 500 mA down to 100 mA, and
3. Change the lower voltage limit from 50 down to 10 V.

The addition of a new software “button” in the main menu screen of the Spectrum toggles the unidirectional setting between ON and OFF. The setting is saved in non-volatile memory so that it is retained while the power is off. The software simply controls the hardware line that activates the relay that controls the unidirectional feature. The software was verified by using an oscilloscope to display the delivered voltage across a load resistor for the ON and OFF settings and cycling of the power.

The changes to allow lower currents are more extensive and include the following:

1. Changes of the parameter selection settings to include currents down to 100 mA.
2. Recalibration of the current setting Pulse Width Modulator (PWM) control.
3. Changing the minimum treatment voltage limit from 50 Volts to 10 Volts.
4. Increasing the tolerance on the internal 300 Load impedance measurement from 10 % to 20%.
5. Disabling one of the redundant Energy monitor circuits.

Changes one and two were simple changes to internal tables that specify the allowed range of treatment current and duration. These allow the study to use much lower charge and energy levels than are possible on a standard spECTrum.

The delivered current circuitry utilizes a PWM to set the desired current. In a standard Spectrum, the allowed range is from 500 mA to 900 mA. A linear equation is used to determine the proper PWM setting for the desired current. Extension down to 100 mA required minor changes to the slope and offset of the linear equation (change 3).

The standard Spectrum requires that the delivered voltage be at least 50 Volts (this guarantees that the patient impedance is at least 100 Ohms). This feature detects and notifies the operator when the treatment paddles are shorted together or the current path is too low an impedance due to too much conducting gel etc. Delivery of 100 mA into 100 Ohms requires 10 Volts, so the lower voltage limit has been dropped to 10 Volts (change 4). Before delivery to a patient, the Spectrum delivers energy to an internal 300 Ohm load and verifies that the proper current, voltage,

pulse width, frequency and duration all occur. Dividing the delivered voltage by the delivered current provides a measurement of the 300 Ohm load resistance. For the standard spECTrum, the measured value must be within 10% of 300 Ohms. The PWM allows current to be set in 4 mA steps. This resolution in current constitutes a 5 times larger contribution to measurement error at 100 mA than it does at 500 mA. Similar concerns apply to the voltage measurement circuitry as well, which has a resolution of 0.5 volts. This requires somewhat larger tolerance on the measured values during this delivery test. The allowed impedance measurement variation has been increased to 20% in the FEAST units (change 5). This still puts the unit well within the required regulatory energy measurement specifications of 30% (energy is proportional to impedance).

Finally, the Spectrum includes multiple methods to ensure that excess energy is not delivered to a patient including:

1. Software monitoring of voltage, current, pulse width, frequency and duration during delivery, including verification of all of these measurement functions before treatment of each patient.
2. Independent hardware monitoring of pulse width, frequency, duration and energy, including verification of all of these functions before treatment of each patient.
3. Another software counter that monitors the energy delivery to ensure it does not exceed the expected delivery settings.

The energy monitoring in items 2 and 3 both derive from a hardware circuit that generates a pulse train whose frequency is proportional to delivered power. Counting these pulses measures the energy. The hardware counts the pulses and ensures that the energy does not exceed predetermined safety thresholds. The software (item 3) also counts the pulses as a redundant backup.

When the current setting is much lower than 500 mA, this hardware circuit fails to provide pulses for counting. As a result, the energy measurement is 0. This causes the software backup counter to register an error, since it checks for both too much and too little energy delivery. The hardware counter continues to function as an energy limiting device according to its original design. For FEAST units, the software energy counter has been disabled. This does not compromise the safety, since the

software continues to verify that current, pulse width, frequency and duration are all as specified (within a few percent for each), and that the voltage does not exceed the limit of 400 volts. This is equivalent to measuring the delivery energy. The software counter was originally included as a means to provide a simple measure of the delivered energy. This is done in the FEAST units by calculating the delivered energy from the previously mentioned parameters including the measured delivery voltage.

It is our belief that these changes provide a unit suitable for the FEAST studies, without compromising the safety features of the standard Spectrum product.

These changes simply continue the changes of the previously approved IDE. Even though the new FEAST protocol will use only 800 mA, we have maintained the 100 mA minimum rather than develop new FEAST software and hardware. This decision eliminates the need to change existing FEAST devices.

B. Hardware Modification

The modifications to the Spectrum Hardware are the addition of a full wave bridge on the output and a relay to switch between unidirectional (output passes through the bridge) and bidirectional (output bypasses the bridge). Dynamic current, voltage, impedance, pulse width and frequency are still all constantly measured during delivery.

The full wave bridge consists of four 1N4005 diodes connected in a standard bridge configuration. These parts are rated 1 Amp 600 PIV each. (Spectrum output is limited to 800mA at 400V peak for FEAST devices). The stimulus output of the spectrum is connected to a DPDT relay that connects either the rectified output of the bridge or the bi-directional output of the standard Spectrum to the stimulus connector. The stimulus connector is connected so the negative output (cathode) connects to the remote treat handle of the standard hand-held stimulus cable. The Anode connection will be to the anterior electrode. The relay is switched by writing a bit to a latch on the backplane of the Spectrum. An indication of "UNI" for unidirectional and "BI" for bidirectional mode is displayed on the LCD display of the spectrum. Output is verified by observing the output across a fixed resistor with an oscilloscope.

C. Details on Implementation of the Changes in the FEAST Device

Item 21 in the FDA review (6/8/05) addressed the implementation of two parameter changes: lowering of the minimum pulse width and lowering of the minimum current from 500 to 100 mA. The FDA requested specific details on how these changes would be implemented.

Regarding the 0.3 ms pulse width, we mistakenly included this as a new feature for the FEAST IDE. This has been a part of our standard product since July of 2003, both in the U.S. and abroad. FDA reviewed documentation on this change in preparation for the FDA two day audit of MECTA on 9/4/03 and 9/8/03. This change has been widely accepted and used throughout the world (including the U.S.A.) since then with beneficial results and no reported adverse affects.

The minimum current setting is controlled by table values in both the 386 and 80C592 processors. The minimum current setting in each table has been changed in the code for each processor and recompiled. The hardware was originally designed to operate from well below 500 mA current output to 1000 mA current output, even though the original specifications were for 500-800 mA. During testing of the desired 100 mA setting, it was found that the lowest usable current setting was about 140 mA. An op-amp used to provide a full output swing from 0 to 5 volts to cover the output current range of 0 to 1 Amp was not providing rail to rail outputs when operated between 0 and 5 Volts. The solution was to change the op-amp lower rail voltage to -5. This allowed current settings all the way down to 100 mA without problems. See the attached circuit changes for details.

D. Verification and Validation Data for the modified Spectrum 5000Q

Item 22 in the FDA review (6/8/05) requested verification and validation data for the modified Spectrum units.

Since the Spectrum is a mature product, and the change for the FEAST IDE is very minor, the verification and validation activities have been limited to the specific changes made. The FEAST units will go through our standard manual and automated testing done for every unit shipped (modified slightly for the different current range). This testing, coupled with the extensive internal testing done by each unit before each patient treatment, guarantees that each unit is functioning

properly, including all of its backup safety circuits. A copy of the **Overall Quality Plan** is attached. (Appendix A.4)

Verification activities for the lower current limit change were straight forward including:

1. Measurement of various delivered currents (100-400 mA) into various load impedances (100-600 ohms) (see data below). The delivered currents were calculated from measurements of the load impedances with a DMM and delivered voltages with a Tektronix TDS 320 digital storage oscilloscope. These were compared to the specified delivery current and required to be within 10%.
2. Standard automated final testing. One of the automated tests verifies accurate calibration of the delivery current.
3. Standard internal testing done by the instrument prior to every patient treatment verifies that correct currents are being delivered

The following representative data was all taken with a 0.5 second duration setting. The voltages were measured with Tektronix TDS 320 digital oscilloscope. The Load resistances were measured with a Fluke 87 True RMS Multi-meter. The worst case delivery current error is 5.0% for 100 mA into 605 Ohms for 0.3 ms.

Table VD. Representative Data Testing Accuracy of FEAST Device Output

Pulse Width	Freq.	Load Resistance	Volts/Current @ 100 mA	Volts/Current @ 300 mA	Volts/Current @ 500 mA	Volts/Current @ 600 mA	Volts/Current @ 800 mA
0.3 ms	60 Hz	90 Ohms	Won't allow treatment				
0.3 ms	60 Hz	104 Ohms	10.8/104	31.2/300	51.2/492	62.4/600	82.0/788
0.3 ms	60 Hz	201 Ohms	20.4/101	59.2/295	98.0/488	118/587	158/786

Notes:

Worst-case conditions occur for shortest pulse width at highest frequency.

The Spectrum uses adaptive current setting. During the delivery of the first 3 pulses, the delivery current is adjusted to make it as accurate as possible and must be within 22% of the expected value. After the first 3 pulses, the current must be within 10% of the expected value. If the current is more than 10% off on any delivered pulse, the Spectrum automatically terminates delivery and

notifies the operator of an error situation. Further, correct current delivery is checked by the Spectrum before each patient treatment by delivering into an internal 300 ohm resistor and verifying that the delivered voltage across the resistor is correct based upon the delivered current (within 8% of expected voltage). If this test fails, patient treatments are inhibited until this and all other internal tests pass.

These verification activities ensure that the modified Spectrum operates correctly in the 100-400 mA range.

Possible faults in the delivered current level and their consequences include:

1. Delivery system fails to turn off current pulse. Hardware pulse width limiter will automatically turn the pulse off after 2.4 ms and force the Spectrum into its error mode which notifies the operator, forces an internal testing cycle, and inhibits further treatments until all internal tests pass. This backup circuit is automatically tested by the unit before every patient treatment and must be working properly before a treatment will be allowed.
2. Delivery current level is wrong (including being too high). Delivered current is measured on every pulse and must be within tolerance or the delivery will be stopped, the operator will be notified, an internal test cycle will be started, and further treatments will be inhibited until all internal tests pass. The current measurement circuit is tested by the unit before every patient treatment and must be working properly before a treatment will be allowed.
3. Current measurement circuit fails. Delivered current is measured on every pulse and must be within tolerance or the delivery will be stopped, the operator will be notified, an internal test cycle will be started, and further treatments will be inhibited until all internal tests pass. The current measurement circuit is tested by the unit before every patient treatment and must be working properly before a treatment will be allowed. This includes a test at two different currents, both of which must pass.

Verification activities for the voltage limit changes are straight forward including:

1. Verifying the modified Spectrum will not allow any delivery into static impedances below 100 Ohms.

2. Verifying that the modified Spectrum successfully delivers 100 mA into 104 Ohms (10.4 Volts).

See the above data table summarizing these results. These verification activities ensure that the modified Spectrum operates correctly over the required voltage range and will not deliver when the voltage is outside of that range.

Possible faults in the delivered voltage level and their consequences include:

1. Delivered voltage too high (broken delivery cables, poor skin prep, etc.). The Spectrum measures the voltage on every delivered pulse and when it is out of range it will terminate the delivery, notify the user, force an internal test cycle, inhibit further treatments until all internal tests pass. The voltage measurement circuit is tested by the unit before every treatment.
2. Voltage measurement circuit fails and reports a value between 10 and 400 Volts (very unlikely failure mode). The voltage measurement circuit is tested by the unit before each treatment and must read the voltage within 8% of the expected value or treatments will be inhibited. This failure would not be detected until the next internal test cycle after the patient treatment is finished. It is then checked at two different voltage readings. This failure, in conjunction with a poor patient electrode contact, could result in a skin burn for that single treatment.
3. Voltage measurement circuit fails and reports a value below 10 or above 400 Volts. The Spectrum measures the voltage on every delivered pulse and when it is out of range it will terminate the delivery, notify the user, force an internal test cycle, inhibit further treatments until all internal tests pass. The voltage measurement circuit is tested by the unit before every treatment.

As noted under Section V.C above, no changes were made related to the pulse-width, so no additional verification or validation activities have been done in this regard for the FEAST units.

D. Feast Electrodes

The anode electrode will be made of the same material as the conventional Spectrum electrodes (stainless steel) and will be 1.25" in diameter. The commercial Spectrum electrodes are circular and 2" in diameter. The cathode electrode will connect to the handle of the current Spectrum hand held stimulus cable. It will be

made of stainless steel and be rectangular in shape (except for radius corners) and it will be 2" wide and 3" long. It will be made malleable so it can be bent to conform to the relative shape of the patient's head. Standard jell and paste will be used to improve patient contact (just as in the current Spectrum). **See Appendix 4 (Electrode shapes)**

The updated information related to the risk of skin burns was addressed earlier.

VI. Investigator Agreement

A signed Investigator Agreement by each of the active investigators is included in Appendix B. These agreements describe each investigator's qualifications. A copy of each investigator's curriculum vitae is attached. These agreements have been signed by:

[name]
[name]
[name]
[name]
[name].

A blank sample agreement is presented below:

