temporal EEG leads. The lesser involvement of medial temporal structures with the seizures induced by FEAST should result, in turn, in lesser amnestic effects, especially for autobiographical information ([name] et al., 2000a). To accomplish this we propose to compare matched groups of patients who have elected to receive FEAST to non-randomized patients received regular treatment with ultrabrief right unilateral (UB RUL) ECT. Since FEAST delivers an ultra-brief stimulus and an identical titration schedule is used in both groups, the only difference in the stimulation given between the groups will be the features unique to FEAST, i.e., the use of unidirectional stimulation and geometry and positioning of the electrodes. As we will carefully evaluate efficacy, this comparison will provide preliminary (but not definitive) data on whether efficacy is equivalent for FEAST relative to traditional ECT.

In summary, we are confident that FEAST does not increase the risks of ECT. It is simply a form of ECT that is more focal and likely more efficient in seizure induction. We have optimized FEAST's potential for being efficacious by limiting its degree of focality and ensuring that markedly suprathreshold electrical dosage can be administered. By using 1.25" diameter electrodes rather than the earlier 3/4" electrodes, we have demonstrated acceptable impedances and have had no instances of skin burns.

D.3 Titrating in the Current Domain

Another innovation was originally examined in this study. This modification was the use of current or pulse amplitude as the basis for titrating electrical dosage to the patient's seizure threshold. As explained below, we no longer use procedures for titrating in the current domain as part of this study. Our original rationale for this approach and the reasons we no longer include it in the procedures are explained below.

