Across the sites 60 patients will be enrolled to achieve 40 FEAST patients who will fully complete this study at the MUSC Institute of Psychiatry, Brain Stimulation Service (BSS) in Charleston, SC, and at GRU in Augusta, GA and Aiken, SC. At both MUSC and GRU, roughly matched 30 patients (each) will also be recruited from those scheduled to receive UB RUL ECT to obtain a cohort of 40 RUL comparison patients. The FEAST and UB RUL ECT groups must meet identical inclusion/exclusion criteria and will undergo identical evaluation procedures. The only difference between the groups will be that one receives FEAST and other UB RUL ECT. The treatment received by the UB RUL ECT group will not be affected by participating in this protocol. This is an open label, non-randomized, non-masked study. Separate consent forms will be used in each group. We are thus asking FDA permission to study 60 patients with FEAST. An additional 60 patients will be studied who receive conventional ECT. Even though they are getting conventional ECT, they are covered by this FDA IDE as their data will be used for comparison purposes with FEAST.

Patients will be selected from those referred for ECT for the treatment of major depressive episode. To verify diagnosis, the SCID-P will be administered to derive DSM-V diagnosis (unipolar or bipolar major depressive episode) and relevant subtypes and specifiers (American Psychiatric Association, 2013).

Inclusion and exclusion criteria are presented in Table 2. Briefly, patients will be between the ages of 18 and 90 years and will provide informed consent. Exclusions include: history of schizophrenia, schizoaffective disorder or any non-mood disorder psychosis, rapid cycling bipolar disorder, central nervous system illness other than conditions associated with psychotropic exposure, alcohol or substance abuse or dependence in the past 3 months, pregnancy, epilepsy, inability to have stable medications, and ECT within the past six months.

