FEAST and ultrabrief RUL ECT patients will be treated identically except as noted below. The traditional d'Elia electrode placement will be used for UB RUL ECT (American Psychiatric Association, 2001), with the frontotemporal electrode tangential to the midpoint of the line connecting the right auditory tragus and the canthus. The posterior electrode will be tangential to the vertex (midpoint of line connecting nasion and inion). Standard stainless steel 2" diameter electrodes will be used. If it is deemed that patients require a change in ECT modality, a switch to either brief pulse RUL or BL ECT will be implememnted, as clinically indicated.

B.8 Assessment of Efficacy

Clinician ratings. Instruments include the HRSD (24-item) (Hamilton, 1967), MADRS (Montgomery and Asberg, 1979), CGI (severity and improvement) (Guy, 1976), and the GAS (Endicott and Spitzer, 1978). A clinical evaluation team independently completes these scales on the basis of conjoint interviews, both at set time points (preECT baseline, 1-2 days after ECT termination) and the HRSD alone is also completed at spaced intervals (weekly during the ECT course). Interviews usually take place between 10 AM-12 PM to minimize variability due to diurnal variation.

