Patients in the comparison group are selected from those referred for ECT and scheduled to start with ultrabrief, right unilateral (UB RUL) treatment. This treatment is routine in the US and internationally, and is considered to manifest the least short- and long-term cognitive side effects compared to other ECT modalities. Participation in this protocol presents no additional risks.

D. Device and Site Safety

Several procedures will be in place to enhance safety in use of the device at the Institute of Psychiatry at MUSC and the two facilities at the GRU (Augusta, GA and Aiken, SC).

D.1 Controlled Access Area

The device will be used only in the dedicated area used for the delivery of ECT at the Institute of Psychiatry at MUSC on the fifth floor. When not in use, the Spectrum 5000Q FEAST device will be shut off and the room and suite housing it is locked. Identical precautions will be taken in the GRU ECT suites in Augusta, GA and Aiken, SC.

D.2 Device Calibration and Evaluation

All the quality control procedures recommended by the manufacturer in the testing and calibration of the Spectrum 5000Q will be followed, including verifying the correct operation of the circuitry that determine whether bidirectional or unidirectional stimulation is delivered. These assessments of device integrity and calibration will be conducted on each device at each site prior to first use and then again at least every 6 months.

D.3 Screening of Subjects Prior to Treatment

As described above, the screening assessment of potential subjects will identify and exclude from participation individuals with current or past medical conditions that may place them at increased risk for adverse effects from ECT or who are unlikely to benefit. Screening will involve physician evaluation, physical examination, and blood work.

D.4 Conduct of FEAST

The conduct of FEAST is detailed in Section IV.B.6. The procedures are described with respect to all aspects of the administration of FEAST, including management of concomitant medications, provision of anesthesia, stimulus dosing, physiological monitoring, and data logging. Prior to study initiation, training sessions will be held in the use of the Spectrum 5000Q FEAST device with all Study Psychiatrists. The study monitor and sponsor will regularly attend treatment sessions to document compliance with study procedures.

D.5 Adjustment of Stimulation Intensity to Individual Seizure Threshold

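### Comparison patients must already be scheduled to start UB RUL ECT but FEAST patients need not be, so the comparison pool is a modality-restricted subset of the FEAST pool and the intended starting modality should be recorded

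*Combined protocol and SAP*

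**What the plan says.** Section IV.B.1 (Patient Selection) sets one general source for the study: "Patients will be selected from those referred for ECT for the treatment of major depressive episode". It also states that "The FEAST and UB RUL ECT groups must meet identical inclusion/exclusion criteria and will undergo identical evaluation procedures", and that the treatment received is the sole difference between them. For the comparison arm it adds a condition: at both sites "roughly matched 30 patients (each) will also be recruited from those scheduled to receive UB RUL ECT". The Risk Analysis Summary (IV.C.5) says the same: "Patients in the comparison group are selected from those referred for ECT and scheduled to start with ultrabrief, right unilateral (UB RUL) treatment".

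No matching condition is stated for the FEAST arm. Section III.D.2 describes that side as "matched groups of patients who have elected to receive FEAST". Table 2 (IV.B.2) asks that a physician judge ECT to be indicated and names no modality.

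The overview that opens Section IV, before B. Protocol, matches the arms within site on gender, unipolar or bipolar diagnosis, age and baseline mMMS. It explains why randomization was set aside and calls the comparison rough. Section B.15 says the study should yield effect sizes for powering a later randomized trial.

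**The concern.** Being scheduled for UB RUL is an entry condition on one arm only. A patient whom the treating team would have started on some other form of ECT can enter the FEAST arm but cannot enter the comparison arm. If such patients exist and differ in prognosis or cognitive vulnerability, part of that difference would be read as an effect of FEAST.

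The exposure is most direct for HRSD24 efficacy (Hypothesis 4), orientation recovery and CUAMI-SF (Hypothesis 5) and subjective memory (Hypothesis 6). The estimates are meant to be carried forward, so a shift here would pass into the design of the next trial.

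The sponsor already applies this reasoning elsewhere. Section B.2 drops the medication-free requirement partly because imposing it on FEAST patients alone would confound the comparison with UB RUL.

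**Working it through.** **Step 1. Entry conditions side by side**

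| Condition | FEAST | UB RUL comparison |
|---|---|---|
| Referred for ECT for a major depressive episode (B.1) | yes | yes |
| Table 2 criteria, including exclusion of patients needing an especially rapid response | yes | yes |
| Already scheduled to start UB RUL (B.1, C.5) | not stated | required |
| Patient elects FEAST (III.D.2) | yes | no |

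Both arms come from one referral stream under one set of criteria. The comparison pool is that stream cut down by intended modality, so the pools are nested.

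**Step 2. Does anything else in the plan cover intended modality?**

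- Matching (overview of Section IV): gender, diagnosis, age, mMMS. No.
- Hypothesis 1: site, age, gender. No.
- Hypotheses 2 and 3: site, age (percent HRSD24 change is added for 2f). No.
- Hypothesis 4: site, medication resistance, baseline HRSD24. Age, gender, age at onset and episode duration enter only secondary analyses, if pre-screening supports them. No.
- Hypothesis 5: site, age, number of treatments, plus baseline CUAMI-SF for that score. No.
- Hypothesis 6: site, age, percent changes in HRSD24 and CUAMI-SF. No.
- Baseline screen at P < 0.2 (B.15): no consequence is stated if a difference is found, and intended modality is not listed as a recorded variable.

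**Step 3. Possible size for HRSD24.** The plan states no figure to reproduce.

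Inputs:
- post-course SD 11.2, from the 17 pilot patients (III.D.6)
- 40 completers per arm (B.1)
- assumed: fraction f of FEAST patients who would otherwise have started another modality, 10% to 40%
- assumed: difference d in their end-of-course HRSD24, 3 to 8 points

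SE = 11.2 × √(2/40) = 2.50. Bias = f × d. The last column is the two-sided 5% rejection rate under a true null (normal approximation).

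| f | d | Bias (points) | Bias/SE | Rejection rate |
|---|---|---|---|---|
| 0.10 | 3 | 0.3 | 0.12 | 5.2% |
| 0.25 | 5 | 1.25 | 0.50 | 7.9% |
| 0.40 | 8 | 3.2 | 1.28 | 24.8% |

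The last row needs both maxima together. As f goes to zero, so does the bias. The documents do not fix its direction.

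**Step 4. What alignment would cost in numbers.** B.1 enrolls 60 FEAST patients to obtain 40 completers, a completion fraction of 40/60 = 2/3. Assume completion does not depend on intended modality.

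- 10% set aside: 60 × 0.9 × 2/3 = 36
- 40% set aside: 60 × 0.6 × 2/3 = 24
- SE at 36 vs 40: 11.2 × √(1/36 + 1/40) = 2.57
- SE at 24 vs 40: 11.2 × √(1/24 + 1/40) = 2.89

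**The case against.** The strongest reply is that no leak has been shown. UB RUL is described as routine (C.5), and the comparison arm follows routine practice at the two sites (B.6). FEAST is itself presented as a form of RUL ECT (C.3), with the same ultrabrief stimulus and titration schedule. It is not obvious why clinicians would offer it to someone they judged unsuited to UB RUL. Patients needing especially rapid response are excluded from both arms. The protocol also says openly that the study is non-randomized, loosely matched and not definitive on efficacy.

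Much of this stands. Three stronger readings are tempting, and the documents do not support them:

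- A reader might infer that the arms come from separate pools, in contradiction of the identical-criteria sentence. Both groups do face the same Table 2; that sentence is incomplete about sourcing, not false.
- A reader might take B.7, where "a switch to either brief pulse RUL or BL ECT will be implememnted, as clinically indicated", or the list of ECT options in C.2, as evidence of alternative starting choices. Both describe later steps: B.7 a change of modality during treatment, C.2 what is offered to nonremitters after the research phase. No section says how starting modality is chosen at either site, or how often it is something other than UB RUL.
- A reader might infer that confounding by indication enters every contrast. The documents supply no mechanism for Hypotheses 1 to 3, and ictal EEG is the stated primary aim.

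Disclosure does not dispose of the point. It covers the lack of randomization and the loose matching, not a different entry condition. A common source population needs no randomization, so the equipoise argument does not apply to it.

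**Conclusion.** The asymmetry is in the text, and nothing in the matching or the models covers it. The comparison pool is a modality-restricted subset of the FEAST pool, so the claim in B.1 that treatment is the sole difference between the groups is too strong. The consequence is a possible bias of unknown size and direction, most direct for Hypotheses 4 to 6.

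The range of 0.3 to 3.2 HRSD24 points rests on two assumed inputs and an unadjusted SD from a small pilot; the planned repeated-measures model with baseline HRSD24 would have a different standard error. If almost all eligible referrals at the two sites start UB RUL, the bias is near zero. Patient self-selection into FEAST remains in any case.

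The change is still worth making. It is cheap, and intended modality cannot be recovered reliably once FEAST has been elected.

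**What to change.** 1. Add one item to the existing CRF that documents why ECT is indicated (B.2), completed before FEAST is offered: the ECT modality the treating team would otherwise start. Report its distribution in the FEAST arm.
2. In B.15, prespecify that the between-group contrasts for Hypotheses 4 to 6 are also run in FEAST patients whose recorded modality is UB RUL. This is a sensitivity analysis, or the main contrast if few patients are set aside; fix what counts as few before outcomes are seen. Report the effect sizes carried to the later trial from this aligned comparison.
3. In B.1, state the source population for each arm and qualify the claim that treatment is the sole difference.

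The cost is one CRF item, a few sentences and one extra set of analyses. No patient's treatment changes, and FEAST patients with another recorded modality stay in the study and in the full-sample analyses. The downside is precision. The 60 enrolled already allow for attrition to 40, so they hold no spare patients for this purpose. At an assumed 10-40% set aside, about 36 to 24 FEAST patients remain, and at 24 vs 40 the standard error rises from 2.50 to about 2.89 HRSD24 points. For that reason the full-sample contrast should be kept beside the aligned one.
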